7.1.2. LABORATORY DATA

Missing laboratory results will not be replaced.

7.1.3. ADVERSE EVENTS

Solicited Adverse Events:

Daily recording of solicited adverse events: for diary cards indicating the presence or absence of solicited adverse events, for studies using paper diaries which have questions in the CRF indicating the presence or absence of solicited events the following rules are applicable:

Document: \\dccar2dnetvnasc01p-lan1.quintiles.net\cp_ops\PROJECTS\Glaxo SmithKline\GSK216152_WZA10802\SAP
Author: PPD Version Number: 2.0
Version Date: 07DEC2023

Template No: CS_TP_BS016 – Revision 7
Effective Date: 01Nov2021

Reference: CS_WI_BS005

- Denominators for the summary of administration site (or systemic) solicited adverse events will be calculated using the number of participants who respond "Yes" or "No" to the question concerning the occurrence of administration site (or systemic) adverse events.
- When a specific solicited adverse event is marked as having not occurred following a specific vaccination (i.e., SDTM FA.FAOCCUR=N for the specified post-vaccination period for the adverse event in question), all daily measurements will be presented as missing.
- When a specific solicited adverse event is marked as having occurred following a specific vaccination (i.e. SDTM FA.FAOCCUR=Y for the specified post-vaccination period for the adverse event in question), any missing daily recordings will be given imputed values to allow them to contribute to the 'Any' rows but not to specific grade rows of the solicited adverse event summary tables.
- When the occurrence of a specific solicited adverse event is not present (i.e. SDTM FA.FAOCCUR is neither Y nor N for the specified post-vaccination period for the symptom in question) but the group of solicited adverse events (administration site or systemic) is marked as having occurred (i.e. SDTM FA.FAOCCUR=Y), all missing daily recordings will be given imputed values to allow them to contribute to the 'Any' rows but not to specific grade rows of the solicited adverse event summary tables.

The following table shows how participants contribute to each category for a specific solicited adverse event over the Day X to Day Y post-vaccination period:

Solicited adverse event category	Participants included in the calculation of the numerator
Any	All participants with at least one occurrence of the adverse event at grade 1, grade 2, or grade 3 between Day X and Day Y or with the adverse event marked as present and at least one missing daily recording between Day X and Day Y
Grade 1	All participants with at least one occurrence of the adverse event at grade 1, between Day X and Day Y
Grade 2	All participants with at least one occurrence of the adverse event at grade 2 between Day X and Day Y
Grade 3	All participants with at least one occurrence of the adverse event at grade 3 between Day X and Day Y

Unsolicited adverse events

Unsolicited adverse event summaries are including serious adverse events unless specified otherwise.

Document: \\dccar2dnetvnasc01p-lan1.quintiles.net\cp_ops\PROJECTS\Glaxo SmithKline\GSK216152_WZA10802\SAP
Author: PPD Version Number: 2.0
Version Date: 07DEC2023

Template No: CS_TP_BS016 – Revision 7
Effective Date: 01Nov2021

Reference: CS_WI_BS005

Missing severity, relationship with study vaccine, and outcome of unsolicited adverse events will not be replaced and will appear as 'UNKNOWN' in all statistical listings.

7.2. DATA DERIVATION

7.2.1. BODY MASS INDEX

BMI (kg/m²) = weight (kg)/height (m²)

7.2.2. AGE AT VACCINATION IN YEARS

When age at vaccination is to be displayed in years, it will be calculated as the number of complete calendar years between the date of birth and the date of vaccination, divided by 365.25. For example:

DOB = 10SEP1983, Date of vaccination = 09SEP2018 -> Age = 34.998 years

DOB = 10SEP1983, Date of vaccination = 10SEP2018 -> Age = 35.001 years

7.2.3. ONSET DAY

The onset day for an event (e.g., AE, medication, vaccination) is the number of days between the last study vaccination and the start date of the event. This is 1 for an event occurring on the same day as a vaccination (and reported as starting after vaccination).

7.2.4. DURATION OF EVENTS

The duration of an event with a start and end date will be the number of days between the start and end dates plus one day, i.e., an event that starts on 03MAR2018 and ends on 12MAR2018 has a duration of 10 days.

The duration of solicited events will be calculated as the difference between the dates when the first and last symptom reported at grade 1 or higher were observed plus one day (also including days after Day 7 if event is still ongoing).

7.2.5. COUNTING RULES FOR COMBINING SOLICITED AND UNSOLICITED ADVERSE EVENTS

For output combining solicited and unsolicited adverse events, all serious adverse events will be considered systemic events since the administration site flag is not included in the expedited adverse event CRF pages.

Document: \\dccar2dnetvnasc01p-lan1.quintiles.net\cp_ops\PROJECTS\Glaxo SmithKline\GSK216152_WZA10802\SAP
Author: PPD Version Number: 2.0
Version Date: 07DEC2023

Template No: CS_TP_BS016 – Revision 7
Effective Date: 01Nov2021

Reference: CS_WI_BS005

Multiple events with the same preferred term which start on the same day are counted as only one occurrence.

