- GSK will further evaluate the case with the iSRC and GSK Global Safety Board and will take the decision to stop or to restart the study intervention administration. GVGH project physician will inform the IQVIA project lead of the decision and the rationale for the decision and all site staff will be informed about that final decision by IQVIA project lead.

Table 5 Study Holding Rules

Events	Number or % of participants needed to pause administration of study intervention	
	Stage 1 Step 1 and Step 2	Stage 2
1a Death or any life-threatening SAE regardless of causality	≥1	≥1
1b Any non-life-threatening SAE that cannot be reasonably attributed to another cause other than study intervention administration	≥1	≥1
1c Any withdrawal from the study (by Investigator or participant request) following a Grade 3 AE that cannot be reasonably attributed to another cause other than study intervention administration	≥1	≥1
1d.1 Any administration site or general solicited event leading to hospitalization, OR Necrosis at the injection site, each within the 7-day (Days 1 to 7) post-administration period	≥1	≥1
1d.2 Fever >40°C (104°F) within the 7-day (Days 1 to 7) post-administration period	≥1	≥2
2a Any Grade 3 solicited administration site event (lasting 48 h or more) in an investigational group, within the 7-day (Days 1 to 7) post-administration period	≥2	NA
2b Any Grade 3 solicited general AE (lasting 48 h or more) in an investigational group, within the 7-day (Days 1 to 7) post-administration period	≥2	NA
2c Any Grade 3 unsolicited AE in an investigational group, that can be reasonably attributed to the study intervention administration, within the 7-day (Days 1 to 7) post-administration period or Any Grade 3 abnormality in prespecified hematological or biochemical laboratory parameters in an investigational group within the 7-day (Days 1 to 7) post-administration period	≥1	NA

Abbreviations: AE = adverse event; h = hours; SAE = serious adverse event; NA = not applicable

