
 • The term disability means a substantial disruption of a person's ability to conduct normal life functions. • This definition is not intended to include experiences of relatively minor medical significance such as uncomplicated headache, nausea, vomiting, diarrhea, influenza, and accidental trauma (eg, sprained ankle) which may interfere with or prevent everyday life functions but do not constitute a substantial disruption.
e) Abnormal pregnancy outcomes (eg, spontaneous abortion, fetal death, stillbirth, congenital anomalies, ectopic pregnancy)

f) Other situations:

- Medical or scientific judgment should be exercised in deciding whether SAE reporting is appropriate in other situations such as important medical events that may not be immediately life-threatening or result in death or hospitalization but may jeopardize the participant or may require medical or surgical intervention to prevent 1 of the other outcomes listed in the above definition. These events should usually be considered serious.

Examples of such events include invasive or malignant cancers, intensive treatment in an emergency room or at home for allergic bronchospasm, blood dyscrasias or convulsions that do not result in hospitalization, or development of drug dependency or drug abuse.

Solicited Events

Events to be recorded as endpoints in the clinical study. The presence/occurrence/intensity of these events is actively solicited from the participant or an observer during a specified follow-up period following study intervention administration.

Table 17 Solicited Events to be Collected

Solicited administration site events	Pain at administration site
	Redness at administration site
	Swelling at administration site
Solicited systemic events	Fever
	Headache
	Myalgia
	Arthralgia
	Fatigue

Participants will be instructed to measure and record the axilla temperature in the evening. If additional temperature measurements are taken at other times of the day, participants will be instructed to record the highest temperature in the pDiary card.

Unsolicited Events

Any AE reported in addition to those solicited during the clinical study. Also, any 'solicited' symptom with onset outside the specified period of follow-up for solicited symptoms will be reported as unsolicited AEs. Unsolicited events will be collected for 28 days after each study intervention administration (ie, Day 1 to Day 28, Day 57 to Day 84 and Day 169 to Day 196).

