16.1. ADVERSE EVENTS

The analysis of solicited adverse event will be performed in the Solicited Safety Set. The percentage of participants with at least 1 administration site AE (solicited and unsolicited), with at least 1 systemic AE (solicited and unsolicited) and with any AE during the 7-day or the 28-day follow-up period, for each stage, will be tabulated with exact 95% CI after each vaccination and overall. The same calculations will be performed for symptoms rated as grade 3 (severe). This combined analysis of solicited and unsolicited AEs will be performed on the Exposed Set as requested for public disclosure. Solicited

Document: \\dccar2dnetvnasc01p-lan1.quintiles.net\cp_ops\PROJECTS\Glaxo SmithKline\GSK216152_WZA10802\SAP
 Author: PPD Version Number: 2.0
 Version Date: 07DEC2023

Template No: CS_TP_BS016 – Revision 7
 Effective Date: 01Nov2021

Reference: CS_WI_BS005

events and unsolicited AEs will be coded by MedDRA.

The percentage of doses followed by at least 1 administration site AE and by at least 1 systemic AE will be tabulated, overall vaccination course, with exact 95% CI. The same computations will be done for Grade 3 AEs, any unsolicited AEs considered related to vaccination, any Grade 3 unsolicited AEs considered related to vaccination and any AEs resulting in a medically attended visit.

The percentage of participants/doses reporting each individual solicited administration site and systemic AE during the 7-day follow-up period will be tabulated with exact 95% CI as follows:

- Over the 3 doses, the percentage of participants with the symptom and its exact 95% CI.
- Over the 3 doses, the percentage of doses with the symptom and its exact 95% CI.
- At each study dose (visit), the percentage of participants with the symptom and its exact 95% CI.

Occurrence of fever within 7 days post vaccination will be reported per grade, per 0.5°C cumulative increments classes as from $\geq 38^{\circ}\text{C}$ as well as the occurrence of fever $>40^{\circ}\text{C}/104^{\circ}\text{F}$.

Solicited events ongoing after the observation period reported by maximum intensity will be left out of summary tables and only reported in solicited AE listings. Any solicited event with onset day greater than solicited period (i.e., 7 days) will be reported as unsolicited AE and will be included in unsolicited summary tables and listings.

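### In the combined AE tables every SAE is classed as systemic, so a serious unsolicited injection-site reaction cannot reach the administration-site row (minor)

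*SAP*

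**What the plan says.** SAP 7.2.5 sets a counting convention and limits its own scope: "For output combining solicited and unsolicited adverse events". Within that scope, "all serious adverse events will be considered systemic events since the administration site flag is not included in the expedited adverse event CRF pages". The missing CRF flag is the only reason given. Neither that section nor any other provides an exception, whether by preferred term or by medical review.

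The tables concerned are in SAP 16.1. They give "The percentage of participants with at least 1 administration site AE (solicited and unsolicited), with at least 1 systemic AE (solicited and unsolicited"). A third row counts AEs of either kind. Results cover the 7-day or 28-day follow-up, by stage, after each vaccination and overall. The same is repeated for Grade 3. A percentage-of-doses table with the same two rows follows. On population and purpose, the SAP states: "This combined analysis of solicited and unsolicited AEs will be performed on the Exposed Set as requested for public disclosure".

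SAP 7.1.3 puts SAEs on the unsolicited side: "Unsolicited adverse event summaries are including serious adverse events unless specified otherwise".

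Protocol Appendix 3, Table 17, solicits only three local events: pain, "Redness at administration site" and swelling. Appendix 3 treats any other local reaction, or a solicited symptom starting after the solicited period, as unsolicited. Protocol Table 5, holding rule 1d.1, names "Any administration site or general solicited event leading to hospitalization, OR Necrosis at the injection site".

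**The concern.** The administration-site row is meant to cover unsolicited as well as solicited local events. Under the convention, a local event loses its place in that row once it is serious and has no diary record, so the misplaced events are the ones that matter most for local tolerability. Rule 1d.1 shows that the protocol foresees severe local events, and hospitalization is one of the protocol's criteria for seriousness.

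Safety and reactogenicity is the primary objective of this first-in-human study. The combined tables are the ones intended for public disclosure. A reader of those tables alone could see a local reaction reported as a systemic one.

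**Working it through.** The documents give no figure to reproduce. The check has two parts: where each kind of event lands, and how far one event can move a row.

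**1. Where a serious local event lands**

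- *Unsolicited and serious, onset within the 28-day window.* SAP 7.1.3 puts it among the unsolicited events, and SAP 7.2.5 classes it as systemic. No other rule places it in the administration-site row. It is therefore counted as systemic only.
- *Solicited (pain, redness or swelling) and serious.* The diary record supports an administration-site count, while the expedited report is classed as systemic. SAP 7.2.5 does not say how the two records of one event are reconciled. It counts same-term events starting on the same day as one occurrence, but does not say which row keeps it. The outcome is undetermined.
- *Non-serious local event.* The rule does not apply.

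The first case is the definite error.

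**2. Size per event**

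Inputs: planned group sizes from Protocol Table 4. Assumption: exactly one participant has an unsolicited serious local reaction, and that participant has no other administration-site AE in the period. The administration-site row then changes from 1/n to 0/n. For the per-dose table the denominator is 3n, assuming every participant receives all three doses.

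| Group | n | Classed by site, 1/n (exact 95% CI) | As written, 0/n (exact 95% CI) | Per dose, 1/(3n) |
|---|---|---|---|---|
| Low dose, Stage 1 | 4 | 25% (0.6 to 80.6) | 0% (0 to 60.2) | 1/12 = 8.3% |
| Full dose, Stage 1 | 16 | 6.3% (0.2 to 30.2) | 0% (0 to 20.6) | 1/48 = 2.1% |
| Full dose, Stage 2 | 45 | 2.2% (0.1 to 11.8) | 0% (0 to 7.9) | 1/135 = 0.7% |

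The intervals are Clopper-Pearson, the method named in SAP 6.1.

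**3. When those sizes apply**

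The rows count participants with at least one event, so each row has its own condition:

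- Administration-site row: one participant too few only if that participant has no other administration-site AE in the same period.
- Systemic row: one participant too many only if that participant has no other systemic AE in the same period. Fever, headache, myalgia, arthralgia and fatigue are all solicited.
- Any-AE row: no change, because the participant is counted either way.

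The same conditions hold dose by dose in the per-dose table. The values in part 2 are therefore upper bounds per event, and the two rows need not both be wrong.

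**4. What the rule does not touch**

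The solicited tables, the unsolicited tables by SOC and preferred term (SAP 16.1), and the SAE counts and listings (SAP 16.1 and 16.1.2) do not use this convention. MedDRA coding is unchanged; only the row in the combined table is affected. The holding rules in Protocol 4.5.1 are assessed by the Investigator and in the safety evaluations, and do not rest on this table.

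**The case against.** The strongest case for leaving the rule alone is that it is an openly stated convention with a stated reason, confined to a disclosure table. The primary safety analyses in Protocol Table 11 tabulate solicited events, unsolicited AEs and SAEs separately. An unsolicited injection-site necrosis within the 28-day window would appear by name in the unsolicited SOC/PT tables, and if serious also in the SAE counts and listings. Few serious local events are to be expected, and a participant who has one within the solicited week may already be in the administration-site row through diary-recorded pain, redness or swelling. A footnote naming any such event would also prevent misreading. Finally, the physician review in SAP 16.1 serves coding, so asking for a local-versus-systemic judgement adds a step.

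Most of this stands, and it limits the priority. It does not remove the error: if the event occurs, following the SAP as written misclassifies it, and the missing flag does not force that result, because the events are coded in any case.

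Three stronger readings are tempting but unsupported:

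- A reader might infer that serious local reactions disappear from safety reporting or escape oversight. They do not. The event sits in the wrong row of one output, and rule 1d.1 works independently of that output.
- A reader might infer that the disclosed table would show no Grade 3 local reaction where one occurred. That needs the SAE to be Grade 3, which Protocol Appendix 3 says must not be assumed from seriousness, and needs nobody else in the group to have a Grade 3 administration-site AE in the period.
- A reader might infer that a hospitalised solicited local event would certainly appear in both rows. SAP 7.2.5 is silent on that.

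**Conclusion.** The point holds in limited form. In the combined tables of SAP 16.1, a serious unsolicited injection-site reaction is counted as systemic and cannot enter the administration-site row. Each event moves a row by at most one participant: up to 25 points in a group of 4, 6.3 in a group of 16 and 2.2 in a group of 45, with smaller changes per dose. These maxima assume the planned group sizes and no other qualifying event for that participant in the same row and period. If no serious unsolicited local event occurs, this error does not arise. No protocol-defined primary endpoint is altered. Minor priority.

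**What to change.** In SAP 7.2.5, replace the blanket rule as follows:

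- Classify each SAE as administration-site or systemic by its MedDRA preferred term, using a list of injection-site, vaccination-site and administration-site terms fixed before unblinding.
- Send ambiguous terms for a medical check by staff without access to treatment assignments. SAP 4.3 unblinds the IQVIA statistical team at the Day 85 interim analysis, so that team should not make the call.
- Count the SAE in the assigned row only.
- State how a diary record and an expedited report of the same event are reconciled, and which row keeps the event.

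While editing, align the stated SAE source: SAP 16.1.2 identifies SAEs from the Adverse Events page, whereas 7.2.5 refers to the expedited pages.

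The cost is a few sentences, a short term list and a small review step. No new data or CRF change is needed. If the convention is kept, the least that is needed is a footnote to the combined tables that states the rule and identifies any serious local event.

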7.2.6. COUNTING RULES FOR OCCURRENCES OF SOLICITED ADVERSE EVENTS

When the occurrences of solicited adverse events are summarized, each event recorded as having occurred during a specific period will be counted as only one occurrence regardless of the number of days on which it occurs.

For a given participant and the analysis of solicited symptoms within 7 days post-vaccination, missing or non-evaluable measurements will not be replaced. Therefore, the analysis of the solicited adverse events will include only vaccinated participants for doses with documented safety data (i.e., diary card completed). A diary card is considered complete when it has data recorded for all 7 days post vaccination. More specifically the following rules will be used:

- Participants who documented the absence of a solicited symptom after one dose will be considered not having that symptom after that dose.
- Participants who documented the presence of a solicited symptom and fully or partially recorded daily measurement over the solicited period will be included in the summaries at that dose and classified according to their maximum observed daily recording over the solicited period.
- Participants who documented the presence of a solicited symptom after one dose without having recorded any daily measurement will be assigned the value 'UNKNOWN'.
- Doses without diary cards returned will be excluded.

The following table describes the rules in detail to be followed in various possible scenarios:

Solicited Symptom	Occurred?	Daily Measurement Record (D1-D7) Missing?	Grade of non-missing values	Maximum Grade for Summary Tables	Contribute to 'Any' row in Summary Tables
All administration site/systemic AEs	No (as per CRF)	Fully Missing	NA	NA	No
All administration site/ systemic AEs (except Temperature)	Yes (as per CRF)	Fully Missing	NA	UNKNOWN	Yes
	Yes (as per CRF)	Partially Missing	All 0s	UNKNOWN	Yes

Document: \\dccar2dnetvnasc01p-lan1.quintiles.net\cp_ops\PROJECTS\Glaxo SmithKline\GSK216152_WZA10802\SAP
 Author: PPD Version Number: 2.0
 Version Date: 07DEC2023

Template No: CS_TP_BS016 – Revision 7
 Effective Date: 01Nov2021

Reference: CS_WI_BS005

Solicited Symptom	Occurred?	Daily Measurement Record (D1-D7) Missing?	Grade of non-missing values	Maximum Grade for Summary Tables	Contribute to 'Any' row in Summary Tables
	Yes (as per CRF)	Partially Missing	At least one grade $\neq 0$	Maximum grade of non-missing values	Yes
Temperature	Missing (computed variable if value $\geq 38.0^{\circ}\text{C}$)	Fully Missing	NA	UNKNOWN	Yes
	Missing (computed variable if value $\geq 38.0^{\circ}\text{C}$)	Partially Missing	All values $< 38.0^{\circ}\text{C}$	UNKNOWN	Yes
	Yes (computed variable if value $\geq 38.0^{\circ}\text{C}$)	Partially Missing	At least one value $\geq 38.0^{\circ}\text{C}$	Maximum grade of non-missing values	Yes

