9.4.1 Primary Endpoints

The analysis on primary objective will be based on the Solicited, Unsolicited, and Exposed Sets, as indicated in [Table 11](#).

Table 11 Primary Endpoints-Statistical Analyses

Endpoint	Statistical Analysis Methods
Primary safety	
 The number and percentage of participants with at least 1 solicited administration site and systemic event during the 7-day follow-up period will be tabulated by group after each study intervention administration and overall. The same calculations will be performed for symptoms rated as Grade 3. The number and percentage of participants with at least 1 unsolicited adverse event (AE) during the 28-day follow-up period will be tabulated by group after each study intervention administration and overall. The same calculations will be performed for symptoms rated as Grade 3. The percentage of doses associated with at least 1 solicited administration site and systemic event during the 7-day follow-up period will be tabulated for the overall administration course. The same calculations will be performed for symptoms rated as Grade 3. The percentage of doses associated with at least 1 unsolicited AE during the 28-day follow-up period will be tabulated for the overall administration course. The same calculations will be performed for symptoms rated as Grade 3. The number and percentage of participants reporting each individual solicited administration site (ie, injection site pain, erythema [redness], swelling) and systemic event (ie, fever [$\geq 38.0^{\circ}\text{C}$], headache, myalgia, arthralgia, fatigue; any Grade and Grade 3) during the 7-day solicited follow-up period after each study intervention administration and by group will be tabulated. The percentage of doses associated with each individual solicited administration site and systemic event will be tabulated for the overall administration course. Occurrence of fever will be reported as number and percentages of participants reporting temperature $\geq 38^{\circ}\text{C}$ in 0.5°C cumulative increments during the 7-day follow-up period. This will be tabulated for each group after each dose. The number and percentage of participants with at least 1 reported unsolicited AE during the 28-day follow-up period after each study intervention administration and by group, as classified by the Medical Dictionary for Regulatory Activities (MedDRA) preferred term, by system organ class and by group will be tabulated. The same tabulation will be performed for Grade 3 unsolicited AEs and for unsolicited AEs according to relationship to study intervention administration. The number and percentage of participants reporting serious AEs (SAEs) and AEs/SAEs leading to withdrawal from the study and/or withholding doses of study intervention, collected from first study intervention administration up to 28 days after third study intervention administration (Day 1 to Day 197) will be tabulated. The detailed listings will also be produced. For each group, for hematological, renal, and hepatic panel test results at 7 days after each study intervention administration (Day 8, Day 64, and Day 176) and at 28 days after each study intervention administration (Day 29, Day 85, and Day 197), and for other tests at baseline: 
 The percentage of participants having hematological, renal, and hepatic results below or above the laboratory normal ranges will be tabulated by time point.

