9.5 Missing Data

Data from participants who withdraw from the study, including AEs and any follow-up, will be included in the analyses of primary, secondary, and tertiary outcomes. Missing data will not be imputed.

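### SAP 7.1.3 and 7.2.6 give conflicting rules for the same solicited-event tables; where diaries are incomplete, primary reactogenicity percentages depend on which rule is programmed

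*SAP*

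**What the plan says.** Protocol 9.4.1 makes these tables part of the primary analysis. It asks for "The number and percentage of participants with at least 1 solicited administration site and systemic event during the 7-day follow-up period", the same for Grade 3, and each individual symptom (for example "headache, myalgia, arthralgia, fatigue; any Grade and Grade 3"). Two SAP sections then say how to count.

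- **SAP 7.1.3.** "Denominators for the summary of administration site (or systemic) solicited adverse events will be calculated using the number of participants who respond". The response meant is a Yes or a No at class level, taken separately for administration-site and systemic events. If a specific symptom has neither Yes nor No but its class is marked Yes, "all missing daily recordings will be given imputed values to allow them to contribute" to the 'Any' row, though to no grade row. The Grade 1 row holds "All participants with at least one occurrence of the adverse event at grade 1, between Day X and Day Y", and Grades 2 and 3 are defined in the same way.
- **SAP 7.2.6.** Missing measurements are not to be replaced, and only doses with a completed card are analysed: "A diary card is considered complete when it has data recorded for all 7 days post vaccination". The bullets below that sentence keep participants with partly recorded days and have them "classified according to their maximum observed daily recording over the solicited period". In the table that follows, a fully missing temperature record, or a partial one with every reading below 38.0°C, gets grade UNKNOWN and contributes to 'Any'.

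Protocol 9.5 states: "Missing data will not be imputed". SAP 3.3 declares one change from the protocol, the added Entered Set.

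**The concern.** A programmer needs one answer to three questions: who is in the denominator, what a blank counts as, and which grade row a participant enters. The SAP gives two answers to each and does not say which section prevails. Two people following it faithfully could produce different tables for a primary safety endpoint.

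The blank-answer rules matter most, because they can turn the absence of a record into an adverse event. A participant with pain marked Yes and redness and swelling left blank becomes a case of all three under 7.1.3. Someone with no reading of 38.0°C or above who skipped one evening's temperature becomes a fever case under the 7.2.6 table. A choice between the rules made after treatment codes are known would be open to challenge.

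**Working it through.** The plan states no figure to reproduce here, so the check sets the rules side by side and applies both to the same hypothetical data.

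**Step 1. Case by case**

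| Situation | SAP 7.1.3 | SAP 7.2.6 |
|---|---|---|
| Denominator | Yes/No to the class question | Complete 7-day cards (text); partial records kept (bullets and table) |
| Symptom marked Yes, some days missing | In 'Any' | In 'Any' |
| Non-temperature symptom blank, class Yes | In 'Any' | Text: not replaced; no table row |
| Temperature partly missing, all readings <38.0°C, systemic class No | No route into 'Any' | Table: in 'Any' |
| Grade 1 and Grade 2 days in one participant | Both rows | Grade 2 row only |

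The second line is agreement. The other four are conflicts or gaps.

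**Step 2. Inputs**

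Group sizes of 45, 16 and 4 come from Protocol Table 4. Intervals are Clopper-Pearson 95%, as in SAP 6.1. Event and missingness counts are assumptions, because the documents give none.

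**Step 3. Denominator** (45 participants, 18 with an event)

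- 7.1.3: 18/45 = 40.0% (25.7 to 55.7).
- 7.2.6 read literally, 2 incomplete cards dropped: from 16/43 = 37.2% if both held events to 18/43 = 41.9% if neither did.
- 5 dropped: from 13/40 = 32.5% to 18/40 = 45.0%.
- 9 dropped: from 9/36 = 25.0% to 18/36 = 50.0%.
- A Grade 3 percentage moves by the same route. Two Grade 3 participants give 2/45 = 4.4%; with 5 cards dropped, the result runs from 0/40 = 0% to 2/40 = 5.0%.

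**Step 4. Fever, 'Any' row** (45 participants, 2 true fevers; m others miss a temperature day, have all readings below 38.0°C and answered No to the systemic question)

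| m | 7.1.3: 2/45 | 7.2.6 table: (2+m)/45 | 7.2.6 complete cards only: 2/(45−m) |
|---|---|---|---|
| 1 | 4.4% | 6.7% | 4.5% |
| 2 | 4.4% | 8.9% | 4.7% |
| 5 | 4.4% | 15.6% | 5.0% |
| 9 | 4.4% | 24.4% | 5.6% |

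At m = 5 the intervals are 0.5 to 15.1, 6.5 to 29.5 and 0.6 to 16.9. In a group of 4 with no fever, one skipped reading takes 0/4 to 1/4 = 25.0%. In a group of 16 with 1 fever, two skipped readings take 1/16 = 6.25% to 3/16 = 18.75%.

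**Step 5. Grade rows** (45 participants: 8 with Grade 1 only, 8 with Grades 1 and 2, 2 with Grades 1, 2 and 3)

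- 7.1.3: Grade 1 = (8+8+2)/45 = 40.0%; Grade 2 = (8+2)/45 = 22.2%; Grade 3 = 2/45 = 4.4%. The rows sum to 30 for 18 participants.
- 7.2.6: Grade 1 = 8/45 = 17.8%; Grade 2 = 8/45 = 17.8%; Grade 3 = 2/45 = 4.4%. The rows sum to 18.

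The 'Any' count (18) and the Grade 3 count (2) are the same under both, because Grade 3 is the top of the solicited scale.

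**The case against.** The best defence is that 7.2.6 corrects itself. Its bullets are introduced as the more specific rules. They keep partial records and exclude only doses with no returned card, and the table has rows for partly missing data. The Solicited Safety Set in SAP 5.3.2 needs only some solicited data for that dose. On that reading the 7-day sentence is a stray line and nobody is dropped. This largely stands as a reading of intent, but the sentence is still in force as written. The partial-record bullet also covers only participants who reported a symptom, so the status of an incomplete card without events remains unclear.

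The defence is also right that much of the missing-data text agrees, that 7.1.3 partly fills a gap left by 7.2.6, and that Protocol 9.4 sends missing-data procedures to the SAP. In the pain, redness and swelling example, the headline row for at least one administration-site event does not move, because pain already makes that participant a case; only the individual-symptom rows move. Table shells outside the supplied documents may settle the grade layout. None of this answers the temperature rows, which contradict the text of their own section.

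Two stronger readings are tempting. A reader might infer that all three conflicts alter the primary results. They do not: Protocol 9.4.1 asks for any-grade and Grade 3 results, and the grade-row conflict changes neither count. A reader might also infer that a large share of diaries would be lost. If each day were missing independently with probability 1% to 5%, then 1 − 0.99^7 = 6.8% to 1 − 0.95^7 = 30.2% of cards would be incomplete, or 3 to 14 of 45. That rests on an invented rate and on the literal reading that the bullets undercut. It also ignores the reminder calls and home visits in the schedule of activities.

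**Conclusion.** The conflict is real and should be resolved. The denominator and missing-answer rules can change primary 'Any' percentages, and the denominator rule can also change Grade 3 percentages, in both cases only if some diary data are incomplete. With complete diaries, 'Any' and Grade 3 are identical under both sections. The grade-row conflict affects Grade 1 and Grade 2 rows alone.

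The size cannot be derived from the documents. The examples show only that a handful of blanks is enough to matter: five skipped temperature readings in a group of 45 can more than triple the reported fever percentage if the 7.2.6 table is applied. Because no hypotheses are tested and no between-group safety comparisons are planned, the harm is to the accuracy and reproducibility of the descriptive safety profile rather than to an error rate.

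**What to change.** Keep one rule set for the solicited-event tables and delete the conflicting text:

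- Delete the 7-day completeness sentence from 7.2.6.
- Keep the 7.1.3 denominators, set separately for administration-site and systemic events. A single denominator of anyone with any solicited answer would count a participant who answered only one class as a non-case in the other.
- Classify each participant once per symptom and dose, by maximum observed grade.
- Leave a symptom with no Yes/No and no daily value as missing, not 'Any', and say whether that participant stays in the symptom's denominator.
- Replace the temperature rows in 7.2.6: fully missing temperature is missing, and a partial record with all readings below 38.0°C is not counted as fever.
- Retain the rule on which both sections agree: a symptom marked Yes with missing days stays in 'Any'.
- If any imputation is kept, list it in SAP 3.3 as a change from Protocol 9.5.

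The cost is SAP wording, with matching edits to table shells and any code already written; no new data are needed. It should be settled before unblinding. SAP 4.3 unblinds the statistical team at the Day 85 interim analysis, so the safe point is before that.
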